7.2. General Methodology

For FAS and PPS descriptive statistics will be used to summarize patient demographics and baseline characteristics. This will include mean, standard deviation, median and interquartile range, minimum and maximum for continuous variables, and counts and percentages for categorical variables. It is anticipated that SAS 9.4 (SAS Institute Inc., Cary, NC, USA) will be used to perform all statistical analyses. Analysis of endpoints based on comparisons between groups on continuous measurements will be performed by Student's t-test or non-parametric test (Mann-Whitney U test) for normal and non-normal distributions, respectively. Normality will be assessed by means of Shapiro-Wilks test and the p-value will be reported. Categorical variable parameter comparisons will be performed using a Chi-square test, or a Mantel-Haenszel test for trend for ordinal variables

with 3 or more categories. The randomization will ensure the two cohorts will be not different but they will be compared in terms of baseline characteristics to check possible confounding covariate. MMRM models will be used to analyze the primary endpoint, taking into account for multiple measures recorded per patient.

7.3. Center Pooling

The study is a multicenter trial and a multicenter impact on primary outcome will be investigated. A description on primary outcome by sites and a graphical representation of the proportions of safety events for each center will be provided.

7.4. Handling of Missing, Unused, and Spurious Data and Dropouts

Outliers and influential observations will be identified via graphical plots and according to study team decision the analysis could be repeated excluding potential outliers.

If the proportion of missing data is less than 10% of data, data will not need a multiple imputation. It is considered that the missing data mechanisms and the missing data patterns have greater impact on research results than does the proportion of missing data when lower than 10% on this sample. In case of missing data greater than 10% and a missing pattern at random, the imputation of missing data will be performed using the most appropriate method depending on the pattern of missing in the data and the type of the imputed variable. The outcome variable will not be imputed. After the imputation of the missing values the models will be rerun.

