9.13. Subject Withdrawal or Discontinuation

Every attempt should be made to follow all treated subjects through study closure.

Upon exiting from the study, no further study data will be collected or study visits will occur for the subject. No study specific medical care will be provided for subjects after the study has been completed and subject will be treated according to the standard routine practice after the study period.

All data available through the time of the subject's exit will be used for analysis. In the event of study exit, the investigator should discuss with the subject the plans for future care and treatment. The investigator should explain that the subject will continue to receive standard medical care. Alternative treatment, such as medication options, or follow-up through standard of care procedures instead of study procedures, and medical consequences should also be discussed. The investigator must notify the subject of any significant new findings that may become available during the course of the study, which are pertinent to the safety and well-being of the subject.

Exit

Subjects may be exited from the study for any of the following situations:

- Subject does not meet inclusion/exclusion criteria and has not been treated
- No BKP or VP attempted
- Procedure attempted but no bone cement was injected
- Subject chooses to withdraw from the study
- Investigator deems withdrawal necessary (medically justified or inclusion/exclusion criteria not met, failure of subject to maintain adequate study compliance)

In the event that a subject is exited from the study prior to study closure, all efforts should be made to continue following the subject until all unresolved procedure or product related adverse events are resolved or they are ongoing and no further actions will be taken.

Lost to Follow-up

In the case that the subject is determined to be lost to follow-up, details of a minimum of three attempts and the method of attempt (e.g., one letter and two phone records or two letters and one phone record) to contact the subject must be recorded. In addition, the requirements set by the governing EC/IRB for subjects lost to follow-up must be followed.

10. Risks and Benefits

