The analyses based on freedom from event at 6 months will be described by means of Kaplan-Meier curves. Cox models will be fitted and hazard ratios (HRs) with 95% confidence intervals will be computed. The proportional hazard assumptions will be tested by means of Schoenfeld residuals. The exposure time (months) will be computed from the date of the index procedure to the date of the last available follow-up or date of first event: [(data end – data in)/30.4].

The rate of event will be computed and reported separately for each group, together with their 95% confidence intervals. Rates were compared by means of either a mixed Poisson model or a negative binomial regression model (if over dispersion was present). Incident rate ratios (IRRs) and 95% confidence intervals were used to compare the two groups.

Analysis of endpoints based on comparisons between groups on continuous measurements will be performed by Student's t-test or non-parametric test (Mann-Whitney U test) for normal and non-normal distributions, respectively. Normality will be assessed by means of Shapiro-Wilks test and the p-value will be reported. Categorical variable parameter comparisons will be performed using a Chi-square test, or a Mantel-Haenszel test for trend for ordinal variables with 3 or more categories.

The analysis on the first primary endpoint based on NRS will use one measure per patient and the comparison will be between the average NRS in both groups. It will be claimed that XPEDE is not inferior to MENDEC with respect to NRS score if the upper bound of the two-sided 95% confidence interval of the difference ($\mu_X(t) - \mu_M(t)$) is less than the margin.

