The analysis on the second primary endpoint based on Index Vertebral Body Angles will use multiple data points per patient according to the number of levels treated. Assuming not completely independence among measures within same patient the analysis will be performed by means of Generalized Estimating Equation (or mixed models for repeated measures) using patient as the subject. The model will have the Index Vertebral Body Angles as dependent variables and baseline value, number of level treated (as the multiple data points) and arm as explanatory variables. All assumptions for regression models will be assessed by viewing plots of the residual values. It will be claimed that XPEDE is not inferior to MENDEC with respect to Angulation if the upper bound of the two-sided 95% confidence interval of the difference ($\mu_X(t) - \mu_M(t)$) is less than the margin.

The overall study is considered reached if both the null NI hypotheses are rejected. A separate Statistical Analysis Plan (SAP) will be developed prior to data being analyzed to further describe statistical methods, pre-specified data handling rules, and pre-specified analyses that will be included in the final study reports. Any deviation from the pre-specified statistical analyses will be noted in the study report.

The Statistical Analysis Plan will include a comprehensive description of the statistical methods and analyses to be included in reports that include analysis of endpoints. Any change to the data analysis methods described in the CIP will require an amendment only if it changes a principal feature of the CIP. Any other change to the data analysis methods described in the CIP, and the justification for making the change, will be described in the clinical study report.

14. Ethics

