7.1.3. Analysis Sets

The analysis will be performed according the Intention To Treat (ITT) principle and a Per Protocol Set will be used as deemed appropriate. The following subject sets will be used for the analysis respectively:

The ITT analysis will use the Full Analysis Set (FAS), which includes all patients enrolled in the study, signed the Informed Consent, were randomized and received the study treatment.

- The Per Protocol Set (PPS) includes all patients enrolled in the study that meet the inclusion/exclusion criteria with no major protocol deviation (see section 7.1.2) that could impact the clinic outcomes and have 6 months follow-up visits completed. The PPS will be used as secondary analysis.

For those patients who drop out of the study, the analyses will include all data up to the point of their last data collection.

The table below shows which population should be used for each of the planned analysis.

Population set	Baseline assessment	Primary Endpoint	Secondary Endpoints	Safety
ITT	✓	✓	✓	✓*
PP	✓	✓		

*in case of patients enrolled but not randomized, a listing of all the adverse events occurred will be presented.

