7.9.1. Primary Endpoint

The primary endpoint is composed by two co-primary endpoints and it is considered reached if both the two co-primary endpoints are met.

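### SAP and CIP conflict on imputing the outcome, no listed analysis tests assumptions about missing 6-month outcomes, and for NRS the text conflicts on whether dropouts' earlier scores enter the primary estimate

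*SAP*

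**What the plan says.** **Imputation.** SAP 7.4 sets a threshold: "If the proportion of missing data is less than 10% of data, data will not need a multiple imputation". Above 10%, and if the pattern is at random, missing values are imputed by a method chosen later. It then adds: "The outcome variable will not be imputed. After the imputation of the missing values the models will be rerun". CIP 13.4 has the same impute-and-refit rule but does not exclude the outcome. It names no method either.

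**Expected loss.** CIP 13.1.2 allows for 15% loss on NRS, and CIP 13.2.2 allows for 20% of treated levels on angle.

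**Dropouts' data in general.** For patients who drop out, SAP 7.1.3 says "the analyses will include all data up to the point of their last data collection". CIP 9.13 says "All data available through the time of the subject's exit will be used for analysis".

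**NRS model.** CIP 13.4: "The analysis on the first primary endpoint based on NRS will use one measure per patient", comparing the group averages. SAP 7.2: "MMRM models will be used to analyze the primary endpoint, taking into account for multiple measures recorded per patient". The same SAP section also gives a t-test or Mann-Whitney rule for continuous endpoints. SAP 7.9.1.1 states the confidence-interval criterion and names no model.

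**Angle model.** CIP 13.4 says the angle analysis "will use multiple data points per patient according to the number of levels treated". SAP 7.9.1.2 agrees: GEE or a mixed model with baseline, number of levels, procedure type and arm, and no visit term.

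**Other analyses listed.** These are a per-protocol set restricted to patients with a completed 6-month visit, the absolute 6-month NRS, two angle t-tests, and an optional rerun without outliers.

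**The concern.** Three gaps meet at the 6-month outcome on which both non-inferiority claims rest.

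1. Protocol and SAP differ on whether a missing outcome may be imputed. At the planned loss (15% and 20%, both above the 10% threshold), the SAP's imputation step is triggered but cannot touch the variable that matters.
2. For NRS, one analyst could run a 6-month completer comparison and another a longitudinal model, and both could cite the plan. The first discards the 1-day and 3-month scores of everyone lost before 6 months. The second uses them.
3. Under either model, nothing shows how bad the unobserved outcomes would have to be to overturn the claim.

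The direction matters. If XPEDE patients who do badly are lost more often than Mendec patients who do badly, a completer comparison understates the true difference and non-inferiority becomes easier to claim. The opposite pattern makes the test conservative.

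**Working it through.** **Plan's own figures.** NRS: margin 1.5, SD 3.27, one-sided 0.025, power 80%, true difference 0. A t-based calculation gives 76 per arm (152), power 80.2%. 152/0.85 = 178.8, so 179, then 180 for 18 strata. Angle: margin 2.5, SD 5.6 gives 160 levels, 160/0.80 = 200, and 200/1.35 = 148 patients. All match CIP 13.1.2 and 13.2.2. With 15% loss from 180, 90 × 0.85 = 76.5 per arm remain, power 80.5%. The issue is therefore bias, not power.

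**Do the listed analyses cover it?**

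| Analysis | Varies the assumption about missing 6-month outcomes? |
|---|---|
| Per-protocol set | No: 6-month completers only |
| Absolute 6-month NRS | No: needs the same 6-month score |
| Angle t-tests | No: only change how levels are combined |
| Outlier rerun | No: removes data |
| CIP 13.4 impute-and-refit | No: one unnamed method, no range of assumptions, outcome barred by the SAP |
| SAP 7.9.2 longitudinal model | No: secondary, lists baseline and arm only, no visit or arm-by-visit term |

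**NRS completer comparison, assumed shift.** Assumptions: true difference 1.5 among all randomised, 15% loss per arm, SD 3.27 for the compared quantity, Mendec dropouts like Mendec completers, XPEDE dropouts worse than XPEDE completers by d.

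- SE = 3.27 × √(2/76.5) = 0.529
- Bias = 0.15 × d
- Error = Φ(0.15d/0.529 − 1.96)
- Between-arm gap among dropouts = 1.5 + 0.85d

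| d | Bias | Gap among dropouts | One-sided error | If reversed |
|---|---|---|---|---|
| 1 | 0.15 | 2.35 | 4.7% | 1.2% |
| 2 | 0.30 | 3.20 | 8.2% | 0.6% |
| 3 | 0.45 | 4.05 | 13.4% | 0.2% |

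The same shift in both arms leaves 2.5%. At 9% loss, just under the SAP threshold (81.9 per arm, SE 0.511), bias = 0.09 × (gap − 1.5)/0.91. Gaps of 2, 3 and 4 points then give 3.1%, 4.7% and 7.0%.

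These are errors for NRS alone. If angle is truly equal and independent of NRS, with independent levels, angle power is 0.875. Overall false success is then 0.875 × (4.7%, 8.2%, 13.4%) = 4.1%, 7.2%, 11.7%.

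**Loss that depends on an observed score.** Simulation, 20,000 trials per setting, 90 per arm, true difference 1.5, 15% loss per arm, random in Mendec, logistic in 3-month NRS in XPEDE. Ranges cover 3-to-6-month correlations of 0.5 and 0.7.

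| XPEDE log-odds per SD | Completer error | Likelihood estimate using 3-month score |
|---|---|---|
| +0.5 | about 4% to 5% | about 2.5% |
| +1 | about 6% to 8% | about 2.5% |

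A repeat at +1 and correlation 0.7 gave 8.7%, so the upper end is approximate. The same mechanism in both arms leaves the completer analysis near 2.5%.

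**Tipping point, NRS.** Shift needed = (1.5 − observed − 1.96 × SE)/loss. At 15% loss:

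- observed 0: (1.5 − 1.036)/0.15 = 3.1 points
- observed 0.2: (1.3 − 1.036)/0.15 = 1.8 points

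Imputation variance lowers these slightly, to 2.9 and 1.7. At 9% loss they are 5.5 and 3.3.

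**Angle.** No error rate is given because the unfavourable direction is unsettled. At 20% loss a 2-degree shift moves the difference by 0.20 × 2 = 0.4 degree. Its sign depends on whether CIP 9.8 (kyphosis negative) or CIP 13.2.2 (smaller is better) governs.

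**The case against.** - **The angle text does not conflict in the way the NRS text does.** This stands. A reader might infer an equal conflict, because SAP 7.2 names MMRM for the primary endpoint and SAP 7.9.1 says "The primary endpoint is composed by two co-primary endpoints and it is considered reached if both the two co-primary endpoints are met". But the two angle-specific passages agree on treated levels, and the multiple measures in SAP 7.2 can be read as those levels. SAP 7.1.3 and CIP 9.13 speak of analysis in general, and the secondary models could be said to satisfy them. What remains is a tension: a level with no 6-month reading adds nothing to the co-primary estimate.
- **Not imputing the outcome is proper in an MMRM.** This also stands. If SAP 7.2 governs NRS over visits, SAP 7.4 is acceptable for the main estimate and only the sensitivity analysis is missing. The inflated errors belong to the completer reading. The text does not settle which reading applies.
- **CIP 13.4 already plans imputation.** A reader of the SAP alone might conclude that imputing the outcome was never planned. The CIP does not support that. But its rule names no method, tests no departure from its assumption, and contradicts the SAP.
- **Strongly arm-specific loss is unlikely.** The documents describe two very similar PMMA cements in a single-blind trial with blinded reading and a wide 6-month window (SAP 7.12). Disposition is reported by arm (SAP 7.1.1). This lowers the likelihood or makes such loss visible. It does not measure its effect. The 15% and 20% are planning allowances, not forecasts.
- **A repeated-measures model would not remove the 4.7% to 13.4% figures.** Correct. It corrects loss explained by observed visits. Shifts in unobserved outcomes need the tipping-point analysis, which informs judgement but does not change the primary test's error.

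**Conclusion.** The point holds in three parts: the SAP and CIP contradict each other on imputing the outcome, no listed analysis varies the assumption about missing 6-month outcomes, and the NRS primary estimate is described in two incompatible ways. For angle there is only a tension with general statements.

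The size is conditional. It needs a completer analysis and loss that is informative in XPEDE only, and every dropout pattern used here is an assumption. A reader might infer that the trial's false-success rate is inflated as planned. The documents do not support that: equal loss patterns leave 2.5%, the reverse is conservative, and both co-primaries must be met. At the planned difference of 0, the roughly 3-point tipping shift (about 0.95 SD) would make the NRS claim fairly robust. At an observed difference of 0.2 the shift falls to about 1.8 points. The plan as written would report neither figure. This should be corrected. Confidence is medium, because the likelihood of arm-specific loss cannot be judged from the documents.

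**What to change.** 1. **Name the estimator.** For NRS, reconcile CIP 13.4 with SAP 7.2 and 7.9.1.1: the primary estimate is the 6-month arm contrast from a likelihood-based repeated-measures model over 1 day, 3 months and 6 months, with baseline, arm, visit and arm-by-visit. For angle, keep levels nested in patient, add the earlier visits so that SAP 7.1.3 and CIP 9.13 are honoured, and use the mixed model already permitted. Unweighted GEE needs data missing completely at random.
2. **Reconcile the imputation rules** in CIP 13.4 and SAP 7.4, and limit the no-imputation sentence to that primary model.
3. **Add one pre-specified delta-adjusted (tipping-point) sensitivity analysis** for missing 6-month NRS and angle, reported whatever the missing fraction. The angle shift must run in the unfavourable direction, so the separate sign conflict between CIP 9.8 and 13.2.2 has to be settled first.

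Cost: SAP wording and programming. If replacing the one-measure NRS comparison counts as a principal feature under CIP 13.4, it also needs a CIP amendment with the approvals in CIP 15.4. The 1-day and 3-month values are already collected, so no new data, patients or visits are needed.

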7.5. Adjustments for Multiple Comparisons

No adjustments for multiple comparisons or multiple look at data will be performed.

7.6. Demographic and Other Baseline Characteristics

Descriptive statistics by group will be used to summarize demographic and baseline characteristic variables for both FAS and PPS. This will include mean, standard deviation, median and interquartile range (IQR), minimum, and maximum for continuous variables, and counts and percentages for categorical variables. Demographic and Baseline variables will be collected through: Medical history, Demographic information, Physical Exam, MRI scan, Study Procedure, AP/Lateral X-ray, Concomitant specific medication, NRS, ODI SF36 questionnaire.

7.7. Treatment Characteristics

Duration of Study Exposure will be measured in days starting from the point of enrollment (informed consent completed and inclusion/exclusion criteria confirmed per the screening evaluation) through and including the time of study exit: Duration of study exposure (days) = (Study Exit date – date of enrollment). Extent of study exposure will be presented in a summary table and supporting data listing.

7.8. Interim Analyses

Interim analyses are not planned for this study.

7.9. Evaluation of Objectives

In this section a detailed information about each objective is included together with calculations and derivations of outcome parameters, analysis methods, datasets analyzed (FAS or PPS).

7.9.1. Primary Endpoint

The primary endpoint is composed by two co-primary endpoints and it is considered reached if both the two co-primary endpoints are met.

7.9.1.1. Primary Endpoint on NRS

The primary endpoint on NRS is the mean change of NRS score from baseline at 6 months post operation in subjects treated with Kyphon®Xpede™Bone Cement compared with subjects treated with Mendec Spine Bone Cement. It will be claimed that XPEDE is not inferior to MENDEC with respect to NRS score if the upper bound of the two-sided 95% confidence interval of the difference (Mean NRS in the XPEDE arm at 6 months - Mean NRS in the MENDEC arm at 6 months) < 1.5 (see an example in section 10.2).

Both change from baseline to 6 months (primary analysis) and absolute value at 6 months (sensitivity analysis) will be reported and analyzed.

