9.3. Stratification and Treatment Assignment

Randomization will be performed according to a randomization schedule developed by the sponsor or sponsor's representative after the subject has signed the Informed Consent and prior to the surgical procedure. The clinical database will contain the randomization distribution system which will be used for this study.

Individuals who are randomized and receive the study treatment will be considered study (treated) subjects; only data from study (treated) subjects will be included in endpoint analysis.

Patients will be randomized 1:1 to either Xpede™ Bone Cement or Mendec bone cement. The sequence of treatments will be randomly permuted in blocks of 2 or 4 patients per block. The blocked randomization will be centralized and schedules will be created by the study statistician using statistical software. The randomization will be performed by the center via the EDC system (Oracle Clinic). To minimize the selection bias, the randomization procedure for this study will use the site (3 sites), the number of vertebral to be treated (1,2 or 3) and the type of procedure (2 procedure: VP and BKP) as stratification factors, so that there will be a separate permuted block randomization list for each stratum (18). This guarantees treatment balance within strata.

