13.1.2. Sample Size Calculations

Sample size calculations were performed in SAS software (SAS Institute Inc., Cary, NC, USA). A sample size is determined such that the non-inferiority of the primary objective is demonstrated that results are not appreciably worse in XPEDE arm compared to MENDEC Spine arm. Based on this information the assumptions for the sample size are:

¹¹ Gemma Marcucci, Maria Luisa Brandi. Kyphoplasty and vertebroplasty in the management of osteoporosis with subsequent vertebral compression fractures. Clinical Cases in Mineral and Bone Metabolism 2010; 7(1): 51-60

¹² Maiettini D., Orgera G., Bisaccia M., Piscitelli L., Laurino F., Meccariello L., Rebonato S., Schiaroli E., Rossi M. and Rebonato A.. Percutaneous Vertebroplasty Improves Pain Control and Quality of Life in Patients Suffering from Back Pain: A Single Center Experience.

¹³ Feng C., Yong-Hui X., Wen-Zhen C., Wei S., Yang G., Bo F. and Difei W. Percutaneous kyphoplasty for the treatment of spinal metastases. ONCOLOGY LETTERS 11: 1799-1806, 2016

¹⁴ Dohm M, Black CM, Dacre A, Tillman JB, Fueredi G; KAVIAR investigators. A randomized trial comparing balloon kyphoplasty and vertebroplasty for vertebral compression fractures due to osteoporosis. AJNR Am J Neuroradiol. 2014 Dec;35(12):2227-36.

- The NRS score which ranges from 0 to 10 is assumed to be approximately normally distributed.
- The NRS score is to be assessed at 24 weeks (6 months) after the procedure.
- The NRS at 24 weeks (6 months) is expected to be 3.5 in the MENDEC Spine treatment, and 3.5 or more in the Xpede. A difference in NRS score of 1.5 or less is considered clinically unimportant for this comparison¹⁵. It is considered the maximum acceptable increase in NRS score compared to the MENDEC Spine arm.
- The standard deviation of the NRS score is expected to be approximately 3.27 (the highest value from the literatures sited above) for each treatment. Common standard deviation will be assumed for both arms.
- The sample size should be sufficient to produce an 80% chance (power) of a significant result at a one-sided 0.025 significance level.

The non-inferiority margin "m" that characterizes the largest absolute difference considered to be dismissible is defined as 1.5. Since smaller values of NRS are better, the hypotheses are based on lower-tailed test:

$$H_0: \mu_X(t) \geq \mu_M(t) + m \quad \text{vs} \quad H_A: \mu_X(t) < \mu_M(t) + m$$

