Where: t is 24 weeks (6 months), μ_X is the NRS mean score in the Xpede arm, μ_M is the NRS mean score in the MENDEC and "m" is the non-inferiority margin.

Based on this statistical test and assuming a one-sided type I error rate of 0.025 and a type II error rate of 0.20 or equivalently, power of 0.80 for the final analysis, it will be claimed that Xpede is not inferior to MENDEC with respect to NRS score if the upper bound of the two-sided 95% confidence interval of the difference ($\mu_X(t) - \mu_M(t)$) is less than the margin.

Thus, the non-inferiority hypothesis will require a sample size of 152 (76 per arm) subjects and including 15% of potential loss-to-follow-up, the total sample size for the study will be 179. If we use 3 * 3 * 2 strata, the sample size should be 180 to be divisible of 18 (90 per arm).

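### The plan does not fix which NRS result decides non-inferiority: change is labelled primary, the rule tests 6-month means, the method texts differ, and none names baseline NRS or the stratification factors

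*SAP*

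**What the plan says.** **Quantity.** Protocol 5.2.1 and SAP 4.1 define the endpoint as change in NRS from baseline to 6 months. SAP 7.9.1.1 ranks the two candidates: "Both change from baseline to 6 months (primary analysis) and absolute value at 6 months (sensitivity analysis) will be reported and analyzed". Its claim rule, however, needs the upper 95% bound to satisfy ("Mean NRS in the XPEDE arm at 6 months - Mean NRS in the MENDEC arm at 6 months) < 1.5". In the protocol 13.1.2 hypotheses the Xpede parameter "is the NRS mean score in the Xpede arm", and the sizing is on the same scale: "The standard deviation of the NRS score is expected to be approximately 3.27".

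**Method.** SAP 7.9.1.1 names no test or model. Three other texts bear on it:
- Protocol 13.4: the NRS analysis "will use one measure per patient and the comparison will be between the average NRS in both groups".
- SAP 7.2: "MMRM models will be used to analyze the primary endpoint, taking into account for multiple measures recorded per patient". It lists no visits or covariates.
- The general default in SAP 7.2 and protocol 13.4: Student's t-test or "non-parametric test (Mann-Whitney U test) for normal and non-normal distributions, respectively", chosen by a Shapiro-Wilk test.

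**Covariates.** Protocol 9.3 stratifies randomization by site, number of vertebrae and "the type of procedure (2 procedure: VP and BKP) as stratification factors". No text on the primary NRS analysis names baseline NRS, levels or procedure. Site appears only in a centre-effect investigation (protocol 13.3) and a descriptive summary (SAP 7.3). The angle model in SAP 7.9.1.2 names baseline, levels and procedure, but not site.

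**Missing data.** Protocol 13.4 provides for imputation, SAP 7.4 rules out imputing the outcome, and SAP 7.1.3 keeps data collected before dropout.

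**The concern.** Both co-primary endpoints must succeed, so the NRS verdict can decide the trial. Read literally, SAP 7.9.1.1 tests the quantity that it calls a sensitivity analysis. Two quantities and several methods are left open, and SAP 7.13 lets the analysis depart from the protocol with justification in the final report. The decisive result could therefore be settled after the data are seen.

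The method matters too. Mann-Whitney yields no confidence interval for a difference in means to set against 1.5. The choice between one measure per patient and a repeated-measures model also decides whether a patient without a 6-month NRS contributes anything. No sensitivity analysis for informative dropout is planned, although 15% loss is budgeted.

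**Working it through.** **1. The plan's own figure.** Inputs from protocol 13.1.2: margin 1.5, SD 3.27, true difference 0, one-sided 0.025, power 80%. The noncentral t gives 76 per arm (152 in total) with power 80.2%. Then 152/0.85 = 178.8, so 179. The stated size is reproduced, and it is the size for the 6-month score.

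**2. Power of the candidate analyses at 76 per arm.** Baseline SD s0 is 0.78 to 1.2, the range in protocol 13.1.1. The correlation ρ between baseline and 6 months is not in the documents and is assumed.
- SD of change = √(s0² + 3.27² − 2·ρ·s0·3.27). Example: s0 = 1.2, ρ = 0 gives √(1.44 + 10.69) = 3.48.
- Baseline-adjusted (ANCOVA) SD = 3.27·√(1 − ρ²), 149 df.

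| ρ | 6-month means | Change, s0 = 0.78 | Change, s0 = 1.2 | ANCOVA |
|---|---|---|---|---|
| 0 | 80.2% | 78.0% | 75.1% | 80.2% |
| 0.1 | 80.2% | 79.9% | 77.9% | 80.6% |
| 0.2 | 80.2% | 81.7% | 80.7% | 81.8% |
| 0.3 | 80.2% | 83.6% | 83.6% | 83.8% |
| 0.5 | 80.2% | 87.4% | 89.4% | 90.0% |

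Change beats raw means once ρ exceeds s0/(2 × 3.27), which is 0.12 for s0 = 0.78 and 0.18 for s0 = 1.2. Apart from a negligible loss of degrees of freedom, ANCOVA is no worse than either.

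**3. How often the two rules disagree.** Bivariate normal simulation, 60,000 trials per setting, 6-month SD 3.27, ρ from 0 to 0.5, s0 0.78 and 1.2:
- True difference 0: opposite verdicts in 5.3% to 10.6%.
- True difference 0.5: 7.6% to 14.7%.
- True difference 1.5 (the margin): at least one rule passes in 3.0% to 3.5%, against 2.5%.

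If the baseline SD were also 3.27 (ρ from 0.2 to 0.7), disagreement at no true difference would be 20% to 29% and the either-passes error 4.2% to 4.8%. Change would then have 60% power at ρ = 0.2.

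**4. Normality switch.** On simulated integer 0–10 scores (76 patients, assumed baseline mean 7.5, ρ = 0.2), Shapiro-Wilk rejects in at least 99% of 6-month samples and 65% to 96% of change samples. If the default applied, it would usually lead to Mann-Whitney.

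**5. Missing 6-month values, illustration only.** Under the one-measure reading, suppose 15% are lost and only Xpede dropouts are worse, by δ points. The bias is 0.15·δ and the standard error is 3.27·√(2/76) = 0.530. One-sided error = Φ(0.15·δ/0.530 − 1.96), which is 4.7%, 8.2% and 13.3% for δ = 1, 2 and 3.

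**The case against.** - **The label already decides.** SAP 7.9.1.1 calls change primary, and the objectives and endpoints agree, so testing raw means would override a written label. This narrows the defect to a contradiction rather than silence. It does not remove it, because the rule that defines success is on the other quantity.
- **The contrasts share one target.** Under randomization, change, 6-month means and an adjusted model all estimate the same mean difference, so 1.5 serves each. Omitting covariates costs precision and does not bias the comparison. That stands, but verdicts in a single trial can still differ.
- **Specific text overrides general text.** The NRS interval rule may displace the t-test/Mann-Whitney default, and the MMRM sentence may mean the multi-level angle model. Both readings are reasonable; no text confirms either.
- **SAP 7.9.2 already has a suitable model.** It gives a GEE or mixed model over 1 day, 3 and 6 months, with NRS as outcome and baseline and arm as terms. It sits under secondary endpoints, SAP 7.2 does not refer to it, and it names no stratification factor. It does make the repair easier.
- **The sizes mix sources.** The baseline SDs are VAS values from studies with postoperative SDs of 1.09 to 1.63, while 3.27 comes from another trial. With each study's own pair, disagreement is at most about 0.2% at no true difference, though it reaches about 8% at a difference of 0.5. Power exceeds 99% if the 6-month SD is 1.63. The power differences therefore matter only near the planned SD, which is the sponsor's own assumption.
- **Imputation is a separate topic.** SAP 7.4 can be read as refining protocol 13.4. Even so, the chosen NRS model determines how missing 6-month values are handled, so the two are best settled together.

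**Conclusion.** The concern holds. SAP 7.9.1.1 contradicts itself on the deciding quantity, the method texts do not agree, and no primary NRS text names baseline NRS or uses the stratification factors for adjustment.

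The effect is moderate. At the planned SD of 3.27 and the literature baseline SDs, the two rules conflict in roughly one trial in ten to one in twenty when the cements are equal. Free choice between them raises one-sided error by 0.5 to 1.0 percentage point. These sizes depend on a baseline SD and a correlation that the documents do not establish for this trial: they would be larger with a baseline SD near 3.27, and disagreement at no true difference would nearly vanish with a 6-month SD of 1.63 or less. The textual contradiction depends on none of these assumptions. It should be corrected before the data are analysed.

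**What to change.** - In SAP 7.9.1.1, name one primary NRS model: MMRM over 1 day, 3 and 6 months with arm, visit, arm-by-visit, baseline NRS, site, number of levels and procedure. Test the adjusted 6-month difference against 1.5. With baseline in the model, the change and absolute contrasts coincide.
- Align SAP 7.2 and protocol 13.4 with this, and cross-refer to the model in SAP 7.9.2.
- State that the Shapiro-Wilk/Mann-Whitney switch does not apply to the primary endpoints.
- Add site to the angle model in SAP 7.9.1.2, so that both co-primary models reflect the randomization.
- Reconcile protocol 13.4 with SAP 7.4 on imputing the outcome, and add one delta-adjusted imputation sensitivity analysis for missing 6-month NRS.

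The cost is wording and one or two extra tables. No new data are needed, since baseline NRS and the strata are already collected. Sparse strata, such as three-level patients, may need pooling; the pooling rule should be written in advance.
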